Screening is conducted by staff via the phone or face-to-face interview in a private area. Study visits (including consenting) take place in the lab and are restricted to authorized personnel only.

As part of Texas Health Presbyterian Hospital Dallas, we utilize two identifiers (name and date of birth) to process subject samples through the IEEM biochemistry lab.

All data collected will be de-identified and only research personnel will have access. All digital recordings will be locked and password protected. Paper records will be handled as stated above. After three years, if the information is no longer needed, it will be shredded or otherwise appropriately destroyed so as to be unreadable. However, any time information is collected; there is a potential risk for loss of confidentiality. Every effort will be made to keep information confidential; however, this cannot be guaranteed.

13. Potential Benefits:

We do not anticipate that individuals participating in the research will receive any direct benefit.

As a result of the proposed studies, upon the completion of this objective, the Department of Defense will be provided with critical information regarding improved care of the hemorrhaging victim in a pre-hospital setting. Combat injuries associated with hemorrhage are almost always accompanied with severe acute pain. This project focuses on evaluating analgesics employed by combat medics in the pre-hospital setting, with an objective of identifying the/those analgesic(s) that do not, or only minimally, impair tolerance to a simulated hemorrhagic challenge in humans. Since hemorrhage is often encountered on the battlefield, it is imperative that the administered analgesic does not impede physiological responses that protect against ensuing hypovolemic shock. That is, the optimal analgesic used for battlefield trauma should provide pain control without impeding appropriate physiological responses to hemorrhage. The proposed experiments will serve to identify the effects of three currently recommended analgesics in the pre-hospital setting (morphine, fentanyl, and ketamine) on tolerance to a simulated hemorrhage in conscious humans. The proposed work will also explore possible sex differences that may affect one's ability to compensate for a hemorrhagic challenge while receiving each of these three analgesics.

With regard to those outside the military, the experiments outlined in this application will determine the effect of currently employed pain medications on tolerance to a simulated hemorrhage in humans. These data will identify the pain medication that least compromises a human's ability to tolerate such an insult, thereby providing critical information to the pre-hospital medics on which pain medication should be employed for such an injury. Obtaining these data will be the first step in the continuum of research that will culminate in an increased understanding of the link between analgesia and hemorrhage. Moreover, the proposed work is particularly unique in that it will be the first investigation conducted in conscious humans to identify the optimal pain medication that will only minimally impair compensatory responses to a hemorrhagic injury, and thus the ability to "survive" that insult. This information will be valuable to both the military and civilian populations as it will improve pre-hospital care of the hemorrhaging victim.

14. Biostatistics:

Not applicable – This project was peer reviewed by the Department of Defense (US Army)

15. References

1. Bellamy RF. The causes of death in conventional land warfare: implications for combat casualty care research. *Mil Med.* 1984 Feb;149(2):55–62.

Analgesics in the Pre-hospital Setting: Implications on Hemorrhage Tolerance - Ketamine

NCT03621085

Document Date: August 30, 2021

Statistical Analysis Plan

Statistical analysis

The primary outcome variables are tolerance to the LBNP challenge with and without analgesic administration, as well as the hemodynamic and autonomic responses to the simulated hemorrhage insult. The effects of any specific drug on LBNP tolerance will be evaluated via a paired T-test (i.e., placebo versus drug). The enrolled subject will not be required to participate in the trials for all three drugs, but they will be required to complete both the placebo and drug trial for each specific drug. To determine which study drug is the least detrimental on tolerance to the simulated hemorrhagic insult, and thus would be recommended to be employed for a soldier experiencing a hemorrhagic injury, we will use one way ANOVA to compare the magnitude of reduction in LBNP tolerance between each drug and the respective placebo condition.

The effects of the administered drugs on hemodynamic and autonomic responses to each LBNP stage will be compared via two way mixed model ANOVA design, with main factors of drug and LBNP level (analyzed both by stage and by % completion of the entire LBNP protocol to pre-syncope). A significant interaction from those ANOVAs will be further explored via pairwise multiple comparison analyses.

Analysis assumptions will be carefully evaluated, data transformations considered, and Bonferroni-Hochberg will be used to adjust for multiple testing as appropriate.

Justification of sample size

No study has evaluated the effects of analgesics on LBNP tolerance in humans. The power and sample size estimates are based on findings from [name] laboratory showing reduced LBNP tolerance in the heat-stressed individuals. In that study heat stressed reduced LBNP tolerance by ~70% (997 cumulative stress index units to 303 cumulative stress index units; $P < 0.001$). Though we expect the analgesics to likewise reduce LBNP tolerance, we do not anticipate as large of a reduction as that observed with heat stress. Thus, the sample size calculation was based upon an anticipated reduction in LBNP tolerance of half that seen with heat stress, i.e., ~35% reduction in the cumulative stress index. Given this anticipated outcome, coupled with the associated variances observed in that study (101), we anticipate 15 subjects per drug trial will be sufficient to address the primary hypothesis that the administered analgesic reduces tolerance to a simulated hemorrhagic insult, with a study power=0.80 at an adjusted alpha=0.015 to account for comparisons between drugs. That value was inflated to 30 subjects in total (15 male and 15 female) to permit a comparison in the primary responses between sexes for each of the administered drugs. That said, interim power analyses will be performed, with the number of required subjects adjusted based upon the variance of the obtained data.

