We propose that if sufficient doses of commonly employed analgesics are administered to humans, otherwise appropriate cardiovascular responses to the hemorrhagic insult will be suppressed, thereby reducing the ability of the individual to tolerate that insult. That said, the effects of analgesic doses of such agents (i.e., doses that are recommended for the pre-hospital setting) on physiological responses necessary to preserve tolerance to a hemorrhagic insult in humans is entirely unknown. Moreover, the aforementioned guidelines by the CoTCCC for condition-specific analgesics are not based upon hypothesis driven scientific evidence in humans, but rather primarily from fully anesthetized animals. Thus, the applicability of that research to a soldier experiencing a hemorrhagic injury is questionable and remains a significant gap in the knowledgebase.

3. Concise Summary of Project:

Three separate protocols, one for each analgesic—fentanyl, morphine, and ketamine will be employed.

Up to five laboratory visits will be required for this protocol.

The first visit will begin with the consenting process. Should the interested subject qualify and agree to participate in the study, he/she will undergo up to four separate experimental visits (up to two placebo and up to two ketamine) each conducted on different days.

Two lower-body negative pressure experimental visits: After instrumentation, subjects will rest quietly followed by baseline data collection and then assessments of pain (via algometer, thermal grill, and the cold pressor test; order randomized). Subjects will then receive the drug along with the progressive lower-body negative pressure (LBNP). If necessary, after waiting for the effects of the first administration of this drug to subside, the drug will again be administered, followed by a recording of post-drug data and re-performance of the pain assessments. For the placebo trial, saline (sodium chloride 0.9% or if unavailable, 5% dextrose in water) will be administered where “Drug Administration” is indicated below. The enrolled subject will be asked to complete both placebo and drug challenges.

Following instrumentation and a quiet resting period, baseline data will be obtained. Then the doses of the analgesic (or placebo) will be administered, with these doses being consistent with the US Army's CoTCCC guidelines (10): Ketamine: (placebo and 20 mg intravenous). Subjects will then rest in the supine position.

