- 45 min: drug administration (placebo or ketamine) followed by progressive LBNP to the onset of syncope signs/symptoms (blood pressure, cardiac output, forearm blood flow, cerebral blood flow, pulse oximeter, blood samples collected; heart rate, muscle sympathetic nerve activity measured continuously)
- 60 min: recovery
- 30 min: drug administration (placebo or ketamine) data collection followed by pain assessments (cold pressor test, thermal grill illusion, and pressure algometry)
- 60 min: recovery followed by pain assessments (cold pressor test, thermal grill illusion, and pressure algometry)

Visits 4 and 5 (resting control experimental visits) – 2 visits (up to ~4 hours each visit)

- 15 min: urine sample (pregnancy test, if applicable), nude body weight measurement, instrumentation with ECG and blood pressure cuff
- 90 min: supine position assumed, insertion of an IV catheter in a vein of the arm, and muscle sympathetic nerve activity signal obtained
- 30 min: baseline data collection
- 45 min: drug administration (placebo or ketamine) and supine rest
- 60 min: recovery

Primary Outcome Variables

The primary outcome variable will be the ability to tolerate the LBNP challenge prior to the onset of signs and symptoms associated with ensuing syncope.

Study Endpoints

Data collection will end when 30 subjects (15 men and 15 women) have completed the experimental protocol and when up to 15 participants complete the resting control experimental protocol.

Sample Size Justification

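### The rule for ordering the placebo and ketamine LBNP visits is not stated and the primary paired t-test has no period term, so a visit effect can bias the drug estimate or cost a little precision (minor; cheap to fix).

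*SAP*

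**What the plan says.** Protocol section 3 (Concise Summary of Project) says that a qualifying subject can expect that "he/she will undergo up to four separate experimental visits (up to two placebo and up to two ketamine) each conducted on different days". The Chronological Detail gives visits 2 and 3 one shared description: "drug administration (placebo or ketamine) followed by progressive LBNP to the onset of syncope signs/symptoms". Neither visit is tied to one condition. SAP, Statistical analysis, adds that subjects need not take part for all three drugs but "they will be required to complete both the placebo and drug trial for each specific drug".

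The only statement about randomised order is in Protocol section 3 and covers the three pain tests within a visit: "via algometer, thermal grill, and the cold pressor test; order randomized". Protocol section 14 (Biostatistics) is marked not applicable, with the remark "This project was peer reviewed by the Department of Defense (US Army".

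For the primary outcome the SAP says "The effects of any specific drug on LBNP tolerance will be evaluated via a paired T-test (i.e., placebo versus drug". Its only mixed model is for the hemodynamic and autonomic responses, "with main factors of drug and LBNP level". No analysis in the SAP contains visit, period or sequence.

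**The concern.** This is a two-period within-subject comparison. The LBNP test runs until signs and symptoms of impending syncope appear, so tolerance could change when the same person is tested again. If more subjects have placebo first than ketamine first, part of that change is counted as a drug effect. With placebo mostly first, better tolerance at the second visit would hide impairment by ketamine, and worse tolerance would mimic it.

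The size of the estimate matters as well as the test. The SAP carries the reduction in tolerance for each drug into a one-way ANOVA meant to show which drug is least detrimental. A shift in ketamine's figure would carry into that comparison.

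**Working it through.** **Inputs from the documents.** SAP, Justification of sample size: 15 subjects, power 0.80, adjusted alpha 0.015, and an "anticipated reduction in LBNP tolerance of half that seen with heat stress, i.e., ~35% reduction in the cumulative stress index". The reference value is 997 units, so the planned effect is 0.35 × 997 = 349 units. Half of the heat-stress reduction, (997 − 303)/2 = 347, is nearly the same. Planned enrolment is 30.

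**Assumed inputs.** Neither document gives a visit effect; I used v = 50, 100 and 200 units (5% to 20% of 997). The SD of the paired difference is also not given. I took 15 as the exact requirement and solved the noncentral t for it: two-sided alpha gives a standardised effect of 0.947, so SD = 349/0.947 = 368. One-sided alpha would give 410; the SAP does not state sidedness. The figure of 15 is therefore reproduced by construction and is not independently verified.

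**Formulas.** Let n1 subjects have placebo first and n2 ketamine first, with n = n1 + n2 and p = n1/n.

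- Bias of the paired mean: v(2p − 1) = v(n1 − n2)/n.
- Expected variance of the differences without a period term: SD² + 4p(1 − p)v² × n/(n − 1).
- Standard error (SE) with a period term: (SD/2) × √(1/n1 + 1/n2), on n − 2 df, with no bias from v as long as both orders occur.

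**Worked case, n = 30, v = 100.**

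- 15:15. Bias 0. Unadjusted SD = √(368.3² + 100² × 30/29) = 382, SE = 382/√30 = 69.8. Adjusted SE = 184.15 × √(2/15) = 67.2.
- 20:10. Bias = 100 × 10/30 = 33. Unadjusted SD = √(368.3² + 0.889 × 100² × 30/29) = 381, SE 69.5. Adjusted SE = 184.15 × √(1/20 + 1/10) = 71.3. Here the period term removes the bias but has the larger SE.

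**Results, n = 30, two-sided alpha 0.015, for v = 50/100/200.** Rejection rates and mean 98.5% confidence interval half-widths are by numerical integration. In the 20:10 power rows, the bias either hides impairment (placebo mostly first and tolerance rising, or the mirror case) or mimics it.

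| Split and measure | Paired t-test | With period |
|---|---|---|
| 15:15, bias (units) | 0/0/0 | 0 |
| 15:15, type I error | 1.4%/1.2%/0.6% | 1.5% |
| 15:15, half-width (units) | 174/179/197 | 173 |
| 15:15, power for 349 units | 0.993/0.991/0.983 | 0.993 |
| 20:10, bias (units) | 17/33/67 | 0 |
| 20:10, type I error | 1.7%/2.2%/3.7% | 1.5% |
| 20:10, half-width (units) | 174/178/about 195 | 183 |
| 20:10, power, bias hides impairment | 0.987/0.973/0.890 | 0.986 |
| 20:10, power, bias mimics impairment | 0.996 or higher | 0.986 |

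The high power in the last row is a product of the bias and is no merit of the test. At 20:10 the period term widens the interval at 50 and 100 units and narrows it only at 200. At 18:12 the bias is one fifth of v: 10/20/40 units.

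**If order were set by an independent coin toss for 30 subjects.** Averaged over possible splits, the paired t-test has mean bias 0, type I error 1.5% and power 0.993/0.990/0.971, against 0.991 with the period term. An exact 15:15 split would occur 14% of the time, 18:12 or more uneven 36%, and 20:10 or more uneven 9.9% (both directions counted).

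**At n = 15** (the number the plan calls sufficient, and the number per sex), an 8:7 split gives power 0.784/0.752/0.638 when the bias hides impairment and 0.802/0.789/0.724 when it mimics it, against 0.789 adjusted.

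**The case against.** The case for leaving the test alone is substantial. No passage shows that a visit effect exists, let alone its size, and 200 units is 57% of the planned drug effect (200/349). Under randomised order the paired t-test is valid on average. At the planned 30 subjects with an even split, even 200 units leaves power at 0.983 with no bias. The period term is not free either: with no visit effect it costs power at an uneven split, and at 20:10 it widens the interval unless the effect is large. All of this stands, and it limits the point to a minor one.

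A reader might go further and infer that everyone had the same order, so that drug and visit are wholly confounded. The documents do not support that. Describing both visits as placebo or ketamine does not suggest a single fixed order, and silence about randomisation does not show that it was absent. Protocol section 8 also refers to a section 4 on study procedures, whose heading does not appear in the text I worked from. The silence is therefore judged on the text as given.

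The objection does not remove the conditional problem. Validity on average over possible splits does not correct the estimate from the one split that occurred, and a reader cannot judge the size of any shift without knowing that split.

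**Conclusion.** The point holds as a minor one. The order rule is not stated in the text available, and no analysis adjusts for period. A visit effect biases the estimated reduction by v(2p − 1) when the realised split is uneven, and makes the test conservative and less precise when it is even. For the planned 30 subjects the effect on the primary test is small unless the visit effect is large or the split uneven. The main gain from adjustment is an estimated reduction, also used in the between-drug ANOVA, that is free of visit bias. A narrower interval is not assured.

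These sizes rest on an assumed additive visit effect of 50 to 200 units, on the back-solved SD of 368, and on no carry-over between visits. It would be wrong to conclude that the comparison is confounded or the paired t-test invalid.

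**What to change.** In the SAP, analyse LBNP tolerance with drug and period (first or second LBNP visit) as fixed effects and subject as a random effect. With complete pairs this is equivalent to regressing the within-subject drug-minus-placebo difference on sequence, coded +1/2 and −1/2, and testing the intercept. Report how many subjects had each order, and say how the order was set. If one order was used for everyone, state that drug and visit effects cannot be separated, since a period term cannot repair that.

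The cost is one degree of freedom and a reported count, with no extra visits or subjects. If there is no visit effect, power for 349 units falls by less than 0.001 at 15:15 and from 0.9935 to 0.986 at 20:10 with 30 subjects, and from 0.80 to 0.73 at 10:5 with 15.

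### The SAP lets a subject enter more than one drug trial, but the Aim 2 one-way ANOVA treats the three sets of reductions as independent

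*SAP*

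**What the plan says.** Protocol Section 1 sets two aims: to test whether each analgesic impairs tolerance to simulated hemorrhage, and to test whether ketamine does so least. Protocol Section 3 describes the structure: "Three separate protocols, one for each analgesic—fentanyl, morphine, and ketamine will be employed".

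The SAP's Statistical analysis section sets the participation rule: "The enrolled subject will not be required to participate in the trials for all three drugs". Anyone who does enter a given drug's trial has to finish its placebo visit as well as its drug visit. So a subject may enter more than one drug trial, and each trial entered brings its own placebo visit.

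Aim 1 uses a paired t-test of placebo against drug, one drug at a time. For Aim 2, "we will use one way ANOVA to compare the magnitude of reduction in LBNP tolerance between each drug and the respective placebo condition". No subject term, repeated-measures form or rule for shared subjects is given. A model that can hold repeated observations is named only for the hemodynamic and autonomic responses, which "will be compared via two way mixed model ANOVA design". The one general safeguard is "Analysis assumptions will be carefully evaluated".

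The documents do not say how many subjects are expected in more than one trial. They give no sample size or power for the between-drug comparison.

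**The concern.** The participation rule and the Aim 2 test stand in the same paragraph and do not fit together. A one-way ANOVA takes all reductions as independent. If the same person supplies a reduction for two drugs, the two values may be correlated, and the variance of the difference between those drugs' means is then not what the ANOVA assumes.

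Aim 2 leads to a recommendation, because the SAP would recommend the least detrimental drug for a hemorrhaging soldier. With positive correlation the p-values for drug differences come out too large, so a worse drug could more easily pass as no different. The comparison of one person under two drugs, which is free of cohort differences, is not used as such. With negative correlation the error runs the other way and false differences become more likely. The stated plan controls neither case.

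**Working it through.** **The plan's own figure.** The SAP gives 15 subjects per drug (power 0.80, alpha 0.015), raised to 30, for placebo versus drug. That is the Aim 1 comparison. It cannot be reproduced, because no SD is given. With a reduction of 347 to 349 units (half of 997 − 303 = 694, or 35% of 997), n = 15 implies an SD of the paired difference of about 366 to 368 two-sided, or 408 to 410 one-sided. There is no Aim 2 figure to reproduce.

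**Inputs for Aim 2.** Overlap is permitted and each drug has its own placebo; both come from the SAP. Three things are assumed:
- equal group size n and equal SD of the reductions across drugs;
- f, the fraction of one drug's subjects who also contribute to the other, from 0 to 1;
- rho, the correlation between one person's reductions on two drugs, from −0.3 to 0.5.

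**Formula.** Each drug's mean reduction has variance SD²/n, whatever the overlap. With f·n shared subjects, the covariance of two drug means is f·n·rho·SD²/n² = f·rho·SD²/n. Hence:
- true variance of the difference = (2·SD²/n)·(1 − f·rho);
- variance assumed by the one-way ANOVA = 2·SD²/n;
- ANOVA SE divided by true SE = 1/sqrt(1 − f·rho).

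**Results.** The last column is the simulated rejection rate of a true null at nominal 5%, with n = 30 per drug, shared subjects in all three drugs and equal correlation.

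| f | rho | 1 − f·rho | SE ratio | Rejection rate |
|---|---|---|---|---|
| 0 | any | 1 | 1.00 | about 5% |
| any | 0 | 1 | 1.00 | about 5% |
| 0.25 | 0.2 | 0.95 | 1.026 | about 4.2% |
| 0.25 | 0.5 | 0.875 | 1.069 | 3.3% |
| 0.5 | 0.2 | 0.90 | 1.054 | about 3.5% |
| 0.5 | 0.5 | 0.75 | 1.155 | 1.9% |
| 1 | 0.5 | 0.50 | 1.414 | 0.3% |
| 0.25 | −0.3 | 1.075 | 0.964 | 6.0% |
| 0.5 | −0.3 | 1.15 | 0.933 | 7.3% |
| 1 | −0.3 | 1.30 | 0.877 | 9.7% |

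Rates at n = 15 are close to these (1.8% at f = 0.5, rho = 0.5). Coverage of a nominal 95% interval for a pairwise contrast at n = 30 is about 97.5% at f = 0.5, rho = 0.5; 99.4% at f = 1, rho = 0.5; and 91.7% at f = 1, rho = −0.3.

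**Power.** Comparisons with a subject-term analysis were run only at full overlap, the extreme case (n = 30, rho = 0.5, nominal 5%). With one drug shifted by 0.5 SD, power is about 42% to 43% for the one-way ANOVA and 79% to 81% with subject modelled. For a shift that has 80% power under independence (0.706 SD), the figures are 85% and 98%. At full overlap the repeated-measures analysis also brings the null rejection rate back to about 5%.

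**The case against.** The strongest reply is that nothing shows overlap will occur. The SAP grants a permission. No section plans, invites or counts shared subjects. The protocol describes separate studies, and Protocol Section 9 recruits from a database of over 2500 people and by public advertising. The fentanyl and morphine protocols, which might govern overlap, are not among the documents. This stands: with no shared subjects the one-way ANOVA has no overlap problem.

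Second, rho may be small. Each reduction is taken against that drug's own placebo visit, which largely subtracts a person's stable tolerance and avoids the correlation that one common placebo visit would force. The drugs also span two classes. This stands as a reason to show a range; at rho = 0.2 and f = 0.25 the SE is off by under 3%.

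Third, with positive rho the error is conservative. That is true, but it does not settle the matter where a finding of no difference would itself inform the choice of drug.

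Fourth, the SAP promises to evaluate assumptions, and independence is one of them. That promise names neither the problem nor a remedy, so it does not close the gap.

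A reader might infer more: that Aim 2 is in fact a partial crossover, or that every error bar involving a shared subject is wrong. The documents do not support either. Overlap is allowed, not designed in, and the variance within each drug is untouched by it. Only between-drug contrasts and the F-test are affected.

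**Conclusion.** The point holds conditionally. The SAP permits shared subjects and names a test for Aim 2 that has no place for them. If f is above 0 and rho is not 0, the between-drug SEs and the F-test are misstated; if either is 0, they are not.

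On the assumptions above, the likely size is modest: an SE overstated by about 3% to 7% at f = 0.25 and 5% to 15% at f = 0.5, for rho between 0.2 and 0.5. The 41% figure, and the near-doubling of power for a 0.5 SD shift, need full overlap with rho = 0.5, and the SAP says that full participation is not required. They mark the outer edge and are not expected values. Positive rho seems the more plausible, which means lost power and not false claims of a difference. Negative rho would reverse that, with up to about 9.7% rejection at nominal 5% (f = 1, rho = −0.3). The Aim 1 conclusions do not depend on any of this.

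**What to change.** In the SAP, keep the one-way ANOVA for Aim 2 only if no subject contributes to more than one drug. Otherwise, specify a linear mixed model of each subject's reduction (drug minus the placebo of that drug's trial), with drug as a fixed effect and subject as a random effect. A random-intercept variance cannot be negative, so if negative correlation is to be allowed, name an unstructured within-subject covariance instead. The switch depends on enrolment counts and not on outcomes, so it can be fixed in advance.

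State the expected overlap, carry a common de-identified subject code across the three protocols, and report how many subjects contribute to two and to three drugs.

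The cost is SAP wording and the linkage; no new subjects or visits are needed. Two limits should be acknowledged. With few shared subjects the subject variance will be poorly estimated. And the model does not remove cohort differences between subjects who are not shared, so that part of the drug comparison remains a comparison of different groups of people.
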